### **Female Patients:**

- 7. Women of childbearing potential (WOCBP) must have a negative urine or serum/plasma pregnancy test. If the urine test is positive or cannot be confirmed as negative, a serum/plasma pregnancy test will be performed. The serum/plasma pregnancy test must be negative for the patient to be eligible.
- 8. WOCBP (refer to Section 8.3.6) must use adequate contraception Adequate contraception must be maintained throughout the study, starting with the first dose through 5 months after the last dose of UV1 vaccination, nivolumab, or ipilimumab, whichever is administered last. The acceptable contraceptive methods for WOCBP included in the study are:

Combined (estrogen and progestogen containing) hormonal contraception associated with inhibition of ovulation (oral, intravaginal, or transdermal), progestogen-only hormonal contraception associated with inhibition of ovulation (oral, injectable, or implantable), Intrauterine device (IUD), Intrauterine hormone-releasing system (IUS), bilateral tubal occlusion, vasectomized partner (provided that the partner is the sole sexual partner of the WOCBP trial participant and that the vasectomized partner has received medical assessment of the surgical success), or sexual abstinence (if this is the preferred and usual lifestyle of the subject)

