#### 6.1.5 Administration of Study Drugs

The administration of study drugs should be done as the last procedure at each applicable study visit per the schedule of activities (Table 5 and Table 6).

Sargramostim and UV1 should be administered **intradermally** in an area corresponding to McBurney's point (Figure 3) on the right side of the abdomen (or corresponding spot on the left side in case of appendectomy scar). It is important that both injections are strictly intradermal. The utmost care must be taken so no material is administered subcutaneously. When done correctly, a small bleb should appear following the injection. An injection too superficial will result in loss of volume from the injection site during injection or after withdrawal of the needle. All 16 injections (8 sargramostim and 8 UV1) should be injected at the **exact same site**. Permanent marker-pens may be used to ensure that the same site is utilized each time.

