PBMC		Х					Х			X	X (2 nd visit only)		
DTH		Х					X	Х		Х	X (2 nd visit only)		

- Abbreviations: AE = adverse event; C = cycle; D/d = day; DNA = deoxyribonucleic acid; DTH = delayed-type hypersensitivity; ECOG = Eastern Cooperative Oncology Group; FFPE = formalin fixed, paraffin embedded; ICF = Informed Consent Form; iCPD = immune confirmed progressive disease; iRECIST = immune Response Evaluation Criteria in Solid Tumors; PFS = Progression Free Survival; PBMC = peripheral blood mononuclear cell; Q4W = every 4 weeks; SAE = serious adverse event; SNP = single nucleotide polymorphisms; V = visit; w = week.
- a Patients with iCPD per iRECIST will be discontinued from treatment and will proceed into the survival follow-up phase and be contacted per phone (or, at the Investigator's discretion visit the hospital) every 12 weeks until PFS cut-off date is reached (earliest of either 70 PFS events or 18 months post last patient randomized). From the PFS cut-off date, the survival follow-up visits will continue every 6 months for 2 years.

b Local lab analysis for verification of eligibility criteria is required during Screening at Day -14 to -1. See Table 7 for protocol-required safety laboratory assessments.

e WOCBP require negative pregnancy test within 72 hours prior to randomization, at Days 10, 31,52, 73 and at the safety follow-up visit. Additional pregnancy tests according to local regulations for treatment of nivolumab and ipilimumab, if required.

dSee Table 8 for collection of samples for exploratory analysis.

e Patients can be randomized up to 3 days (from Day -3 until Day 1) prior to first dosing on Day 1 but only after all Screening assessments are completed.

- f Patients will start maintenance therapy 6 weeks after last dose of induction therapy.
- g From signing of the ICF until the first dose of induction therapy only AEs/SAEs caused by study-specific procedures should be reported. All non-serious AEs should be reported from the first dose of induction therapy until 30 days after the last dose of induction therapy, or until new anticancer treatment is initiated (whichever comes first). All SAEs should be reported from the first dose of induction therapy until the PFS cut-off date is reached or until new anticancer treatment is initiated (whichever comes first).

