Abbreviations: AE = adverse event; C = cycle; D/d = day; DNA = deoxyribonucleic acid; ECOG = Eastern Cooperative Oncology Group; FFPE = formalin fixed, paraffin embedded; ICF = Informed Consent Form; iCPD = immune confirmed progressive disease; iRECIST = immune Response Evaluation Criteria in Solid Tumors; PFS = Progression Free Survival; PBMC = peripheral blood mononuclear cell; Q4W = every 4 weeks; SAE = serious adverse event; SNP = single nucleotide polymorphisms; V = visit; w = week.

a Patients with iCPD per iRECIST will be discontinued from treatment and will proceed into the survival follow-up phase and be contacted per phone (or, at the Investigator's discretion visit the hospital) every 12 weeks until PFS cut-off date is reached (earliest of either 70 PFS events or 18 months post last patient randomized). From the PFS cut-off date, the survival follow-up visits will continue every 6 months for 2 years.

b Local lab analysis for verification of eligibility criteria is required during Screening at Day -14 to -1. See Table 7 for protocol-required safety laboratory assessments.

c WOCBP require negative pregnancy test within 72 hours prior to randomization, at Days 1, 22, 43, 64 and at the safety follow-up visit. Additional pregnancy tests according to local regulations for treatment of nivolumab and ipilimumab, if required.

d See Table 8 for collection of samples for exploratory analysis.

e Patients can be randomized up to 3 days (from Day -3 until Day 1) prior to first dosing on Day 1 but only after all Screening assessments are completed.

f Patients will start maintenance therapy 6 weeks after last dose of induction therapy.

- g From signing of the ICF until the first dose of induction therapy only AEs/SAEs caused by study-specific procedures should be reported. All non-serious AEs should be reported from the first dose of induction therapy until 30 days after the last dose of induction therapy, or until new anticancer treatment is initiated (whichever comes first). All SAEs should be reported from the first dose of induction therapy until the PFS cut-off date is reached or until new anticancer treatment is initiated (whichever comes first).

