## **Appendix 1 Clinical Laboratory Tests**

- Local laboratory analysis (all patients) are detailed in Table 7.
- Central laboratory sampling for exploratory analysis (all patients) are detailed in Table 8.
- Extended Exploratory Cohort assessments (approximately 40 patients) are detailed in Appendix 2, Table 9, and Table 10.
- Additional tests may be performed at any time during the study as determined necessary by the Investigator or required by local regulations.
- Blood samples must be collected prior to administration of treatment.

Table 7Local Laboratory Analysis (all patients, N=154)

Laboratory Assessments	Parameters		
Hematology	Red blood cell (RBC) Count Hemoglobin Hematocrit White blood cell (WBC) Count Platelet Count Absolute neutrophil count	RBC Indices: Mean corpuscular volume Mean corpuscular hemoglobin	WBC count with Differential: Neutrophils Lymphocytes Monocytes Eosinophils Basophils
Clinical Chemistry from serum or plasma 	Blood urea nitrogen (BUN)/Urea*Glucose (non-fasting) CalciumPotassiumCalciumPotassiumAlkaline phosphataseTotal and direct bilirubinAspartate aminotransferase (AST/GOT)CreatinineAlanine aminotransferase (ALT/GPT)SodiumLactate dehydrogenaseAlbuminUric acidChlorideThyroid panel (TSH and fT4)		
Other Screening Tests	
 
Hepatitis B surface antigen and hepatitis C virus antibody
 
Human chorionic gonadotropin pregnancy test (for women of childbearing potential)
 
		
NOTES:  All events of ALT or AST ≥3 × upper limit of normal (ULN) AND bilirubin ≥2 × ULN, which may indicate severe liver injury (possible Hy's Law), must be reported as a serious adverse event.  Local urine testing will be standard for the protocol unless serum or plasma testing is required by local regulation or Institutional Review Board/Independent Ethics Committee. If the urine test is positive or cannot be confirmed as negative, a serum or plasma pregnancy test will be required. *Assessment of urea to be performed by sites where laboratories are not using BUN. Total amount of blood for local analysis will be approximately 30 mL per patient.			

Investigators must document their review of each laboratory safety report.

Treatment arm	Visits	Laboratory assessments	Volume of blood
			collected

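### Minor, optional safety point: Table 5 sets no pregnancy-test limit at the first UV1 dose, so the last required negative test can be up to 6 days old

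*Combined protocol and SAP*

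**What the plan says.** The Table 5 footnote for the experimental arm reads "WOCBP require negative pregnancy test within 72 hours prior to randomization, at Days 10, 31,52, 73 and at the safety follow-up visit". The Table 5 grid agrees: the pregnancy-test row is marked at Screening, Days 10, 31, 52 and 73 and safety follow-up, and is blank on Day 1. A further Table 5 footnote allows a lead time: "Patients can be randomized up to 3 days (from Day -3 until Day 1) prior to first dosing on Day 1".

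For the control arm, the Table 6 footnote reads "WOCBP require negative pregnancy test within 72 hours prior to randomization, at Days 1, 22, 43, 64 and at the safety follow-up visit", and the Table 6 grid marks Day 1.

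Three other provisions bear on the point:

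- Inclusion criterion 7 (section 5.1) says "Women of childbearing potential (WOCBP) must have a negative urine or serum/plasma pregnancy test". It gives no time limit.
- The Table 5 footnote continues "Additional pregnancy tests according to local regulations for treatment of nivolumab and ipilimumab, if required".
- Appendix 1 says "Additional tests may be performed at any time during the study as determined necessary by the Investigator or required by local regulations".

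Section 2.8 states that there is no information on UV1 and reproduction, and it answers with contraception before, during and after vaccination. Inclusion criterion 8 makes contraception compulsory for women of childbearing potential from the first dose until 5 months after the last.

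**The concern.** UV1 and sargramostim are the investigational products, and in the experimental arm they are given before any checkpoint inhibitor. The 72-hour limit is tied to randomization and not to dosing, and the two can be days apart. A woman can therefore receive her first vaccination on a test that meets every written requirement but is nearly a week old. A pregnancy too early to show on that test might show on a fresher one.

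What is at stake is a small amount of avoidable fetal exposure to a product without reproductive data. Power, type I error and the PFS comparison are not touched.

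**Working it through.** **Inputs**

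- Test to randomization: at most 72 hours = 3 days (Table 5 footnote).
- Randomization to first dose: at most 3 days, Day -3 to Day 1 (Table 5 footnote; sections 4.1 and 4.2).
- First UV1 plus sargramostim dose: Day 1. Two more vaccinations fall within Days 3 to 7 (section 4.1).
- Next required test: Day 10.

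**The plan's own figure.** Screening ends on Day -1 and dosing starts on Day 1, so there is no Day 0. The steps -3 to -2, -2 to -1 and -1 to 1 make 3 days, as stated.

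**Test age at first dose** = days from randomization to Day 1, plus 0 to 3 days.

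| Randomized on | Lead to Day 1 | Age of last required test |
|---|---|---|
| Day -3 | 3 | 3 + 0 to 3 + 3 = 3 to 6 days |
| Day -2 | 2 | 2 to 5 days |
| Day -1 | 1 | 1 to 4 days |
| Day 1 | 0 | 0 to 3 days |

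The overall maximum is 3 + 3 = 6 days (144 hours). In the control arm the Day 1 test makes it 0 days, because section 6.1.5 places dosing at the end of the visit.

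**Does other text shorten this?**

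- Inclusion criterion 7 has no window.
- The extra tests in the Table 5 footnote depend on local rules for nivolumab and ipilimumab, which start on Day 10 in this arm.
- The Appendix 1 clause covers any test but is permissive unless local regulations require one.

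None of these sets a limit at the first dose.

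**Why the arms differ.** Experimental test days 10, 31, 52 and 73 are the nivolumab/ipilimumab days of that arm, and control test days 1, 22, 43 and 64 are those of the control arm. The UV1-only visit on Day 26 has no test either. One rule fits both tables.

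**After each change**

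- Negative test at most 72 hours old at first dose: maximum 3 days. The largest gain is 6 - 3 = 3 days, and it is nil for women randomized on Day 1.
- Pre-dose Day 1 test: 0 days. The largest gain is 6 - 0 = 6 days.

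**Who is left to benefit.** Version 5.0 is dated 22 September 2023. Planned last patient in was H1 2022 for the randomized part and H1 2023 for the single arm cohort. The plan does not expect 70 PFS events before late 2028, so the cut-off should fall 18 months after the last randomization. A readout by the end of June 2024 then puts the last randomization no later than the end of December 2022.

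**The case against.** The strongest reply is that the schedule is deliberate and adequate. Every woman needs a negative test within 72 hours before randomization. Contraception is the protocol's stated answer to the missing reproductive data. Pregnancy stops UV1 (section 7.2.1) and must be reported and followed to outcome (section 8.3.6). Six days requires both extremes at once, and the documents do not say how often the Day -3 allowance is used. The number of women of childbearing potential, the chance of a pregnancy in the window and the sensitivity of the urine test are also not given, so the benefit cannot be quantified.

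Most of this stands, and it is why the point is minor. It does not remove the gap. Contraception under inclusion criterion 8 begins with the first dose, and although section 2.8 extends it to the time before treatment, neither makes the last test more recent.

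A reader might infer three stronger things that the documents do not support:

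- That the sponsor gives controls a protection it withholds from UV1 patients. The control Day 1 test is the Cycle 1 nivolumab/ipilimumab test, and its counterpart in the experimental arm is Day 10. It sets no precedent for testing before UV1.
- That women may be vaccinated without a recent negative test as a matter of course. The pre-randomization test always applies, and the usual age may be well under 6 days.
- That the single arm cohort has no test requirement because it is not randomized. Appendix 7 applies the experimental-arm procedures and the same eligibility criteria, and enrollment through the IWRS is the sensible stand-in. The wording is loose, nothing more.

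**Conclusion.** The gap is real but small. No provision limits the age of the pregnancy test at the first dose of the investigational products, and the last required negative test can then be 0 to 6 days old, depending on the day of randomization. The 6-day figure assumes no Day 0, randomization on Day -3 and a test at the 72-hour limit. The same range holds for the single arm cohort only if enrollment takes the place of randomization with the same Day -3 allowance.

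A fresher test could reveal some early pregnancies that an older one missed. It would not detect conceptions still too recent to show, and it leaves the vaccination schedule before Day 10 as it is. Because planned enrollment dates precede version 5.0, few or no patients may remain to benefit; these are planned dates, and the protocol does not state that enrollment is closed. The change is optional and has no bearing on the efficacy analysis.

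**What to change.** Keep the negative test before randomization (before enrollment in the single arm cohort), and make one of two changes for any remaining enrollment:

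1. Require the latest negative test to be no more than 72 hours old at the first dose of induction therapy, and repeat it if older. The worst case falls to 3 days, and the single arm cohort gains a usable anchor. Controls already comply through their Day 1 test.
2. Add a Day 1 test to the Table 5 grid and footnote. Section 6.1.5 already says "The administration of study drugs should be done as the last procedure at each applicable study visit per the schedule of activities", so the test would come before the dose and the age falls to 0 days.

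The drafting cost is one table row or footnote. In use it is at most one extra test per woman of childbearing potential, at a visit where hematology and chemistry are already scheduled. Appendix 1 keeps it simple: "Local urine testing will be standard for the protocol unless serum or plasma testing is required by local regulation". A positive or unclear urine result needs a serum or plasma test and could delay Day 1 dosing. A woman confirmed pregnant after randomization would remain in the ITT population without being dosed, as would a control with a confirmed positive Day 1 test under the present schedule.

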#### Table 6Schedule of Activities – Control Arm

	Screening		Induction	therapy		Follow-up period				
Visit/Cycle		V1 C1	V2 C2	V3 C3	V4 C4	Safety follow-up	Response follow-up	Survival follow- up a	Survival follow- up a	
Visit window		0	± 2d	± 2d	± 2d	+7d	±1w	±1w	+2w	
Days/Weeks	D -28 to -1	Dl	D22	D43	D64	30 days post last dose of induction therapy	10w post last dose of induction therapy then every 8w for 32w. Subsequent visits every 12w until iCPD per iRECIST or PFS cut-off date reached	Every 12w from iCPD per iRECIST until PFS cut-off date reached	From time of thePFS cut-off date reached: Every 6 months for 2 years	
Signed consent	Х									
Eligibility criteria	X									
Medical history	X									
Vital signs & ECOG	X	Х	Х	Х	Х	Х				
Physical examination	Х					Х				
Local lab analysis (all patients) b			4	1						
• Hematology & chemistry  )	Х	Х	Х	Х	Х	Х				
Hepatitis B & C virus	Х									
Pregnancy test c	Х	Х	Х	Х	Х	Х				
Central lab sampling (all patients) d		Х		Х	Х	Х	X (2 nd visit only)			
Randomization e		Х								
Treatment:										
Nivolumab		Х	Х	Х	Х	Nivolumab 480 mg Q4W according to label (maintenance therapy) f				
• Ipilimumab		Х	Х	Х	Х					
Adverse Events g	Х	Х	Х	Х	Х	Х	Х	Х		
Concomitant medication h	Х	Х	Х	Х	Х	Х				
Subsequent anticancer treatment						Х	Х	Х		
Survival status								Х	X	
Tumor imaging i	FIRST tumor i SECOND tum SUBSEQUEN first)	imaging dur or imaging a T tumor ima	ing Screeni at Week 12 aging every	ng at Days and THIR 8 weeks fo	-14 to -1 D tumor in or 32 week	maging at Weeks and then ev	ek 19 post randomizatio ery 12 weeks until PD p	on per iRECIST or until the PFS cut-c	off date is reached (whichever comes	
Extended Exploratory Coho	ort (40 patients) j									
Signed consent (exploratory cohort)	Х									
Fecal sample	X									
Tumor biopsy (FFPE & snap-frozen) k	X					Х				
DNA & SNP		Х								
PBMC		Х		Х		Х	X (2 nd visit only)			

Abbreviations: AE = adverse event; C = cycle; D/d = day; DNA = deoxyribonucleic acid; ECOG = Eastern Cooperative Oncology Group; FFPE = formalin fixed, paraffin embedded; ICF = Informed Consent Form; iCPD = immune confirmed progressive disease; iRECIST = immune Response Evaluation Criteria in Solid Tumors; PFS = Progression Free Survival; PBMC = peripheral blood mononuclear cell; Q4W = every 4 weeks; SAE = serious adverse event; SNP = single nucleotide polymorphisms; V = visit; w = week.

a Patients with iCPD per iRECIST will be discontinued from treatment and will proceed into the survival follow-up phase and be contacted per phone (or, at the Investigator's discretion visit the hospital) every 12 weeks until PFS cut-off date is reached (earliest of either 70 PFS events or 18 months post last patient randomized). From the PFS cut-off date, the survival follow-up visits will continue every 6 months for 2 years.

b Local lab analysis for verification of eligibility criteria is required during Screening at Day -14 to -1. See Table 7 for protocol-required safety laboratory assessments.

c WOCBP require negative pregnancy test within 72 hours prior to randomization, at Days 1, 22, 43, 64 and at the safety follow-up visit. Additional pregnancy tests according to local regulations for treatment of nivolumab and ipilimumab, if required.

d See Table 8 for collection of samples for exploratory analysis.

e Patients can be randomized up to 3 days (from Day -3 until Day 1) prior to first dosing on Day 1 but only after all Screening assessments are completed.

f Patients will start maintenance therapy 6 weeks after last dose of induction therapy.

- g From signing of the ICF until the first dose of induction therapy only AEs/SAEs caused by study-specific procedures should be reported. All non-serious AEs should be reported from the first dose of induction therapy until 30 days after the last dose of induction therapy, or until new anticancer treatment is initiated (whichever comes first). All SAEs should be reported from the first dose of induction therapy until the PFS cut-off date is reached or until new anticancer treatment is initiated (whichever comes first).
- h All ongoing and new medications will be recorded from 28 days prior to randomization, until 30 days after the last dose of induction, or until new anticancer treatment is initiated (whichever comes first). Ongoing and new medications shall also be recorded in connection with any SAEs.
- i Tumor imaging should be performed regardless of treatment stop or delays and within a visit window of ± 7 days. Tumor imaging will be performed using CT/MRI scans of the chest, abdomen, and pelvis. CT scans are the required modality for measurable disease unless a patient has a clinical condition (e.g. severe contrast allergy) or the lesions are better visualized through the use of MRI. The same imaging technique has to be used in a patient throughout the study. If an unscheduled CT/MRI is performed during the study, subsequent protocol planned CTs/MRIs should be performed unless the time interval between the CTs/MRIs is ≤4 weeks.
- j A cohort of approximately 40 patients at selected sites will be asked to volunteer for additional biological sampling and analysis. A separate ICF will be used for the Extended Exploratory Cohort and will be different than the main study. See Table 9 and Table 10 for collection of samples for the Extended Exploratory Cohort.

k If the patient has only one target lesion, the biopsy should be taken either subsequent or at least 7 days prior to the screening imaging scan.

 It is recommended to have blood sampling on day of treatment. If the sampling was not done on the day of treatment and the most current Liver Function Test (LFT) results warrant a safety concern, the site must repeat the LFT panel on the day of treatment and review the results prior to study drug administration.

# 7.1 Screening

Within 28 days prior to randomization, potential patients will be evaluated to determine if they fulfill the eligibility criteria described in Section 5.1 and Section 5.2. Procedures conducted as part of the patient's routine clinical management (eg, blood count) obtained before signing of the ICF may be utilized for Screening or Baseline purposes provided the procedure met the protocol-specified criteria and was performed within the timeframe defined in the schedule of activities (Table 5 and Table 6).

